particular choice. At the beginning of the task, these Q values are set to zero; after every trial t , the value of the chosen stimulus (e.g., A) will be updated according to the rule $Q_a(t+1)=Q_a(t)+\alpha*\delta(t)$, where $\delta(t)$ is the prediction error [$\delta(t)=R(t)-Q_a(t)$], i.e., the difference between the expected outcome [$Q(t)$] and the actual outcome [$R(t)$]. The reinforcement magnitude R will be +1 and -1 for winning and losing \$1, respectively, and 0 for neutral outcomes. Based on the Q values, the probability of selecting an action will be computed using the softmax rule (Luce, 2003). Next, regressors will be convolved with a canonical hemodynamic response function. Linear contrasts of regression coefficients will be computed at the individual subject level and then taken to a group level random effects analysis. Using linear contrasts, main analyses will investigate representation of prediction errors as well as responses to the stimuli. ROI analyses will be performed with a focus on striatal and prefrontal regions reviewed in Section A.2, followed by whole-brain analyses. Whole-brain data will be thresholded at voxelwise $p < 0.005$ and corrected for multiple comparisons using Gaussian Random Fields. Only clusters significant at $p < 0.05$ (corrected) will be interpreted.

MRS. The acquisition protocol described in a preliminary test-retest reliability MRS 3T study, which has been extensively used at McLean Hospital (e.g., Henry et al., 2011; Jensen et al., 2009; Ongur et al 2008), will be implemented. Using high-resolution, T1-weighted MPRAGE anatomical images, a 2x2x2 cm voxel will be placed over the each subject's rostral anterior cingulated cortex (rACC). The voxel will be shimmed using Siemens' automated shimming routine and the tip-angle, water-suppression, frequency and coil-tuning will be automatically adjusted. A 2D-JPRESS sequence will be used to collect 22 TE-stepped spectra with: TE: 35-350ms (15ms increments, f1 bandwidth: 67Hz); TR: 2s; spectral bandwidth: 1.2 kHz; readout: 512 ms. The resulting 2D-JPRESS spectra will be fitted using LCModel templates. These procedures have shown excellent test-retest reliability (Brennan et al 2010; Jensen et al 2009; Ongur et al 2008). Because MRS cannot distinguish neuronal from non-neuronal sources of Glu, the ratio of Gln to Glu provides the best index of overall glutamatergic transmission. The Gln/Glu ratio within this voxel will be the primary MRS measure of interest.

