Behavioral Data: For the PRT, the main dependent variable will be Reward Learning, as operationalized as the increase in response bias during the final block relative to the first block [= DResponse Bias = Response Bias(Block 3) - Response Bias(Block 1)]. This variable was selected because it has been repeatedly linked to current and future anhedonic symptoms (Pizzagalli et al., 2005, 2008b; Vrieze et al., 2013a).

b. Study endpoints

Not applicable

c. Statistical methods

Data analyses will proceed in two stages. First, descriptive statistics and graphs will be used to assess the presence of skewness and/or outliers in the four main variables of interest (*Aim 1*). Continuous/quantitative variables will be appropriately transformed. Similarly, covariates in regression analyses (*Aims 1 & 2*) will be summarized to determine whether a continuous versus categorical representation is the most appropriate. For these regressions, the analytic approach will address the type of outcome (e.g., continuous or discrete) and the functional relationship between covariates and outcome (e.g., linear versus non-linear). The second stage will involve the analyses of the central hypotheses in *Aims 1-2*:

Aim 1: For Hypothesis 1, we will first use multiple regression to examine the relationships between our behavioral and neuroimaging measures and the symptom domains of anhedonia, mania and impulsivity, which will be assessed using the symptom severity collected during session 2. Standard multiple regression techniques will be used to identify the optimal weights for each unit of analysis (MRS, fMRI striatal PE signals, ERP FRN, PRT response bias). Additionally, to take advantage of the correlations between the three symptom domains and to potentially improve predictive accuracy, a single multivariate analysis (canonical correlation analysis) will be used to assess a separate set of weights reflecting the contribution of each unit in relationship to all three symptom domains simultaneously. For ease of interpretation, the latter analysis will be based on the first pair of canonical variables. Models will be fit using SAS PROC CANCORR.

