Aim 2: For Hypothesis 2a, symptom inventories collected during follow-up interviews will be used to investigate incremental predictive validity of each unit of analysis in predicting subsequent symptoms while controlling for baseline severity. For these models, our behavioral and neuroimaging measures will be modeled using the relative weighting derived from the analyses described in aim 1. For quantitative measures (e.g., depressive and anhedonic symptoms), linear mixed effects models will be used. These models incorporate random subject effects to account for correlation among the repeated outcome measures (months 0, 3, 6); models will be fit using SAS PROC MIXED. Hypotheses concerning frequency measures (e.g., frequency of impulsive/risky behaviors) will be tested in a similar way. Models will be fit using SAS PROC GENMOD. Statistical tests and confidence intervals will be based on the “sandwich” estimator of standard errors to ensure that correlation among repeated assessments and overdispersion is accounted for.

d. Power analysis

Sample size and power calculations

Sample size determination was calculated based on observed effect sizes derived from prior studies that in our lab. Effect sizes were calculated using $\alpha = 0.05$ (two-tailed) for (1) detecting relationships between reward learning variables across different unit of analyses and reward-related symptoms (e.g., anhedonia, mania); and (2) to predict symptom severity measures in a naturalistic follow-up study. Based on these estimates and allowing for 15% patient attrition or data loss, the sample will be: 80 treatment-seeking individuals with mood disorders recruited from three clinics as well as 32 psychiatrically healthy controls.

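### The 5% corrected level for whole-brain fMRI clusters depends on an unchecked spatial noise model; permutation inference would hold the level at little cost

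*Combined protocol and SAP*

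**What the plan says.** The fMRI/MRI paragraphs of section VI.a set out a two-level analysis: "Linear contrasts of regression coefficients will be computed at the individual subject level and then taken to a group level random effects analysis". On what is tested: "Using linear contrasts, main analyses will investigate representation of prediction errors as well as responses to the stimuli". On the order of work: "ROI analyses will be performed with a focus on striatal and prefrontal regions reviewed in Section A.2, followed by whole-brain analyses".

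For the whole-brain step the rule is "Whole-brain data will be thresholded at voxelwise $p < 0.005$ and corrected for multiple comparisons using Gaussian Random Fields", followed by "Only clusters significant at $p < 0.05$ (corrected) will be interpreted".

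The section does not give the functional voxel size, smoothing kernel, software, smoothness estimator, sidedness of the test or number of whole-brain maps. It plans no check of the random field assumptions and names no permutation alternative.

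In section VI.c (Aim 1) the four measures entered in the regressions are "MRS, fMRI striatal PE signals, ERP FRN, PRT response bias". Aim 2 reuses the weights from those regressions. Section VI.d plans for "80 treatment-seeking individuals with mood disorders recruited from three clinics as well as 32 psychiatrically healthy controls", "allowing for 15% patient attrition or data loss".

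**The concern.** Random field correction of cluster extent takes one smoothness estimate and converts it into the cluster size expected by chance. The conversion assumes that spatial correlation falls off as a Gaussian curve and does so equally everywhere. If correlation has a longer tail, or if some regions are smoother than others, chance clusters can be larger than the formula allows. A lenient forming threshold such as p < 0.005 is more exposed than a strict one, because the clusters it forms are larger.

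The corrected p-value is the only filter between a whole-brain map and an interpreted cluster. If it does not deliver 5%, chance clusters for prediction errors or stimulus responses could be reported as circuit findings.

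**Working it through.** **What can be reproduced.** The 5% is a nominal level per map. It cannot be derived from the documents, because smoothness, search volume and sidedness are not given. It can only be tested by simulation under assumptions.

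**Inputs from the plan.** Forming threshold p = 0.005; corrected level 0.05; random-effects group maps; 80 patients and 32 controls (80 × 0.85 = 68 patients after the planned loss; the runs below use 80).

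**Assumed inputs.** Null volumes of 38³ = 54,872 voxels (about 1.5 L at 3 mm); one tail; 2,000 maps per setting; the correlation shapes in the table.

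**Cut-off formula.**
- Smoothness from the lag-1 correlation ρ: FWHM = √(−2 ln 2 / ln ρ). With ρ = 0.823, FWHM = 2.67 voxels.
- Expected number of clusters above u, three-dimensional term: E[m] = V (4 ln 2)^1.5 (u² − 1) exp(−u²/2) / ((2π)² FWHM³). With u = 2.576 and V = 54,872, E[m] = 68.85.
- β = (Γ(5/2) E[m] / (V p))^(2/3) = (1.3293 × 68.85 / 274.36)^(2/3) = 0.481.
- Solve 1 − exp(−E[m] exp(−β k^(2/3))) = 0.05: k = (ln(68.85 / 0.0513) / 0.481)^1.5 = 57.9 voxels. Including the lower-dimensional terms gives 51.8.

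**Results at p < 0.005.** Each pair is three-dimensional term only, then all terms. The simulation standard error is at most 1.1 points.

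| Assumed noise | Estimated FWHM (voxels) | Cut-off (voxels) | Family-wise error | Cut-off that gives 5% |
|---|---|---|---|---|
| Gaussian, FWHM 2.67 | 2.67 | 57.9, 51.8 | 1.8%, 3.4% | 47 |
| Gaussian, FWHM 4 | 4.00 | 147.7, 126.3 | 1.5%, 3.6% | 119 |
| 10% tail exp(−r/3) | 2.58 | 53.6, 48.1 | 4.4%, 7.6% | 52 |
| 30% tail exp(−r/3) | 2.43 | 46.4, 41.9 | 15.1%, 21.3% | 63 |
| 50% tail exp(−r/3) | 2.30 | 40.6, 36.8 | 28.2%, 35.6% | 70 |
| 50% tail exp(−r/4) | 2.50 | 49.5, 44.6 | 31.4%, 38.6% | 100 |
| Half at FWHM 2, half at FWHM 4, pooled estimate | 2.58 | 53.4, 47.9 | 33.7%, 41.9% | 101 |

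For the larger departures the ratio to nominal runs from 15.1/5 = 3.0 to 41.9/5 = 8.4.

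**Sensitivity to the set-up.** Further runs with other grids, kernels and decay lengths gave:
- about 1% to 2% under Gaussian correlation;
- about 3% to 9% with a 10% tail, taking all runs together;
- 15% to 28% with a 30% tail;
- 38% to 59% with a 50% tail;
- 13% to 24% with a smooth wide tail in place of the exponential.

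The direction is stable; the size is not.

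**A stricter threshold alone.** At p < 0.001, still with random field correction, the error was 8.7% to 20.4% with 30% to 50% tails and 21.2% to 24.5% with non-uniform smoothness. That is lower but still above 5%.

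**Permutation.** Two-sample t-maps of 80 v 32 were simulated on a smaller volume (22³ voxels) with a 50% tail exp(−r/3): 1,722 null data sets, 99 label shuffles each, forming threshold p < 0.005. A data set was rejected if the observed maximum cluster was in the top 5% of its own 100 arrangements. Random field correction rejected 20.1% and permutation 4.8% (standard error √(0.048 × 0.952 / 1,722) = 0.5 points).

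**The case against.** The strongest reply is that nothing in the documents shows the noise to depart from the model, or by how much. The tail share, decay length, kernel, grid and formula terms are all assumed. Where the model fits, the plan is conservative. This stands: the calculations describe exposure, not an observed error.

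A second reply is that the exponential has a cusp at distance zero, which lowers the smoothness estimated from neighbouring voxels, so part of the excess may be short-range roughness rather than a long tail. One run supports this: with a 30% tail and FWHM 4, shortening the decay from 5 to 2.5 voxels raised the error from 25% to 36%. It does not remove the point, because a smooth wide tail with no cusp still gave 13% to 24%.

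A third reply is that the consequence is limited. ROI work comes first, and no whole-brain cluster enters the tests of Hypotheses 1 or 2a. This also stands, and it sets the priority.

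A reader might infer that the 5% level holds only if the model fits exactly. That is too strong, since a 10% tail stays near nominal. A reader might also take a twelve-fold excess as the likely size; 59% (59/5 = 11.8) comes from one extreme setting.

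**Conclusion.** The point holds as a conditional weakness of method, not as a contradiction or an arithmetic error in the plan. The stated 5% is secure if the spatial correlation is Gaussian and uniform, and roughly so under slight misfit. Under the larger departures simulated it could be exceeded, mostly by about 3 to 8 times. These sizes rest entirely on assumed correlation shapes, one-tailed maps and assumed volumes.

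The documents do not support saying that this study's clusters will be false, or that its main tests are compromised. The exposure is confined to the secondary whole-brain maps. The plan will nevertheless interpret clusters that pass, and the remedy is inexpensive, so the change is worth making at low to moderate priority.

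**What to change.** In section VI.a, replace the random field step with permutation inference on the maximum cluster size at family-wise p < 0.05. Use sign-flipping for one-sample maps and label shuffling for patient v control maps. Keep the p < 0.005 forming threshold; p < 0.001 is optional, since permutation held its level without it and a stricter threshold loses some sensitivity to broad, weak clusters. State sidedness and the number of whole-brain maps at the same time.

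The cost is a few lines of text and computing time, with no new data or visits. Permutation has its own conditions: symmetric errors for sign-flipping and exchangeability for label shuffling, the latter deserving thought with groups of 80 and 32. Fewer clusters may reach significance where random field correction was too lenient.

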EEG or MRI will complete the following self-report clinical assessments that would have been administered at the EEG session: the Inventory of Depressive Symptomatology (IDS; Rush et al., 1996; the IDS is a self-rated depression symptom severity rating scale); Medical Outcome Survey-Short form (SF-36; McHorney et al.,1993; the SF-36 is a measure of physical functioning, physical role functioning and social functioning); Quality of Life (Q-LES-Q; Endicott et al., 1993; the Q-LES-Q measures patient satisfaction and enjoyment across domains); Mood and Anxiety Symptom Questionnaire (MASQ; Watson et al., 1995; the MASQ is a self-report assessment of anhedonic depression, anxiety symptoms, and general distress); Temporal Experience of Pleasure Scale (TEPS; Gard et al., 2007; the TEPS is a self-report assessment of anticipatory and consummatory (in-the-moment) pleasure experiences); the Perceived Stress Scale (PSS; Cohen et al., 1983; the PSS is a self-report assessment of the degree to which situations in one's life are appraised as stressful within the past month) the MGH Antidepressant Treatment Response Questionnaire (ATRQ; Chandler et al., 2009; the ATRQ assesses treatment history and medication use); the Chapman Handedness Inventory (CHI; Chapman & Chapman, 1987; the CHI is a self-report assessment of handedness); a General Habits Questionnaire (GHQ; the GHQ is a self-report assessment of caffeine intake); a Menstrual Cycle Questionnaire (MCQ; the MCQ is a self-report

of menstrual cycle patterns); the Barratt Impulsiveness Scale (BIS; Patton, Stanford & Barratt, 1995) and the Beck Depression Inventory – II (BDI-II; Beck, Steer, & Brown, 1996; the BDI-II is a self-report assessment of depressive symptomatology).

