For group comparisons, multiple past studies using the PRT have found that unmedicated MDD subjects exhibited reduced reward learning compared to controls (Cohen's $d: -0.70$; Pizzagalli et al 2008c; Cohen's $d: -0.61$; Vrieze et al 2013a). In contrast, euthymic individuals with bipolar disorder had significantly higher reward learning relative to controls (Cohen's $d: 0.72$) (Pizzagalli et al 2008b). For the reinforcement learning task proposed for our fMRI study (Pessiglione et al 2006), we found that, relative to healthy controls, MDD subjects had significantly lower accuracy during reward learning (Cohen's $d: -1.54$). These effect sizes translate to power >0.98 for detecting group differences with the proposed sample size. For dimensional approaches, past studies have shown a strong large effect for the relationship between reward learning and anhedonic symptoms in BPD patients ($r = -0.59$). Moreover, among healthy subjects, reward learning predicted anhedonic symptoms 30-40 days later ($r = -0.41$, $p < 0.05$). In light of these effect sizes, a total of 80 individuals with mood disorders leads to a power of >0.97 of (1) detecting relationships between units of analysis and reward-related symptoms (e.g., anhedonia, mania), and (2) predicting clinical outcome in the naturalistic follow-

up study. Finally, in an fMRI study probing reward processing, unmedicated MDD subjects showed weaker activation than controls to gains in the caudate ($d = -0.98$) and left Nac ($d = -0.73$) and left putamen ($d = -0.78$) during reward anticipation (Pizzagalli et al 2009), yielding a mean effect size of -0.87. In light of an average ES of 0.83 in the fMRI study, a total of 80 individuals with mood disorders and 32 healthy controls leads to a power >0.97 of detecting group differences.

VII. RISKS AND DISCOMFORTS

The risks associated with participation in this study are minimal, and every possible precaution is being taken to further reduce potential risks, as described below:

Behavioral component. We foresee no risks from the behavioral tasks required for the proposed research.

Genetic component.

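### Aim 1 fits four units jointly with default complete-case methods although missing EEG or MRI is foreseen, so the analysed number may fall below the 68 implied by the 15% allowance

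*Combined protocol and SAP*

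**What the plan says.** Section VI.c (Statistical methods, Aim 1) regresses each of three symptom domains, measured at session 2, on four units: MRS, fMRI striatal prediction error, ERP feedback-related negativity and PRT response bias. It then relates all four units to all three domains in a single canonical correlation: "Models will be fit using SAS PROC CANCORR". No missing-data method is given for either analysis.

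The protocol expects some patients to lack units. Under V.a, Session 1, patients who qualify on the PRT but cannot take part in the "EEG or MRI will complete the following self-report clinical assessments that would have been administered at the EEG session". Under V.a, Sessions 2 and 3, a positive or refused urine drug test ends participation. At session 3 the pregnancy rule does so too.

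Section VI.d sizes the study this way: "allowing for 15% patient attrition or data loss, the sample will be: 80 treatment-seeking individuals with mood disorders". It then claims that "a total of 80 individuals with mood disorders leads to a power of >0.97 of (1) detecting relationships between units of analysis" and reward-related symptoms. Hypothesis 1 (Section II) is framed across patients and controls, and there are 32 controls.

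**The concern.** A model that needs four predictors and an outcome from each person discards anyone lacking one of them. The canonical analysis needs all seven variables. Every weight is then estimated on the joint complete cases. This includes the PRT weight, whose measure is the cheapest to obtain and the least likely to be missing.

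The plan has one 15% allowance for all causes, but the units come from two laboratory visits and three recording modalities, so losses accumulate. If the complete-case number is smaller than the planning number, the weights are less precise than the power statement suggests. The Aim 1 weights are also carried into Aim 2, where a weighted combination cannot be formed for a person with a missing unit. If the reason for missing a scan is related to symptoms given the units, the complete-case weights may also be biased; the documents neither show nor exclude this.

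**Working it through.** **Inputs from the documents.** 80 patients, 15% attrition or data loss, alpha 0.05 two-sided (VI.d); prior correlations of -0.59 and -0.41, of which the second is the binding one (VI.d); four units and three symptom domains (VI.c); 32 controls (II).

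**Assumed, not in the documents.** A loss rate f of 5%, 10% or 15%; correlation 0.3 between units; standardised weights of 0.2 each.

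**Step 1: reproduce the stated power.** For one correlation, power = Φ(atanh(r)·√(n−3) − 1.96). With r = 0.41, atanh(r) = 0.4356.
- n = 80: 0.4356 × √77 − 1.96 = 1.86, power 0.969. Simulating the exact test gives 0.970, and a noncentral t calculation gives 0.978.
- At r = 0.59 and n = 80, power is about 1.00.

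The plan's figure above 0.97 is therefore reproduced, to rounding, at the full 80.

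**Step 2: apply the plan's own allowance.** 80 × 0.85 = 68. At n = 68: 0.4356 × √65 − 1.96 = 1.55, power 0.940.

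**Step 3: joint completeness of 80 patients.** fMRI and MRS are acquired in one session, so two patterns bracket the range.

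| f | fMRI and MRS lost together, 80(1−f)² | three independent losses, 80(1−f)³ |
|---|---|---|
| 5% | 72 | 69 |
| 10% | 65 | 58 |
| 15% | 58 | 49 |

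The number reaches 68 when (1−f)² = 0.85, f = 7.8%, or when (1−f)³ = 0.85, f = 5.3%. In both cases no other attrition is counted.

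**Step 4: power at those numbers (r = 0.41).** n = 72: 0.951; 65: 0.929; 58: 0.898; 49: 0.840. Power stays at or above 0.80 down to n = 45. This is the single-correlation basis that the plan uses, not the power for a weight in a four-predictor model.

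**Step 5: with controls.** If all 32 controls enter and lose data at the same rates, the base is 112. By visit, 112(1−f)² gives 101/91/81; independently, 112(1−f)³ gives 96/82/69.

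**Step 6: gain from using all observed data.** Data for 80 people were simulated under the assumed correlations. The SD of the complete-case weights was divided by the SD of the maximum-likelihood weights.

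| Loss pattern | SD ratio at 10% | SD ratio at 15% |
|---|---|---|
| fMRI and MRS lost together | 1.03-1.14 | 1.05-1.15 |
| independent | 1.12-1.15 | 1.14-1.26 |

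The reduction in SD is 1 − 1/ratio. By visit it runs from 1 − 1/1.03 = 3% to 1 − 1/1.15 = 13%. For independent losses it runs from 1 − 1/1.12 = 11% to 1 − 1/1.26 = 21%. When losses are by visit, a large share of the gain goes to the PRT weight.

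**The case against.** A reader might infer that the analysed number must end well below 68. The documents do not support that, for four reasons.

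- No EEG, fMRI or MRS failure rate is given. At 5% loss, both patterns in the working stay above 68.
- The allowance is worded as "allowing for 15% patient attrition or data loss". Data loss is already named in it, so taking modality failures off 68 may count the same loss twice.
- The background section describes the 80 as the neuroimaging sample, and Aim 1 says this sub-sample is tested on all four units. Patients without EEG or MRI may therefore be additional to the 80. Their questionnaires are taken at session 1, whereas Aim 1 uses session 2 scores, and someone with neither EEG nor MRI adds little to the laboratory-unit weights.
- Hypothesis 1 includes controls, so 80 need not be the base.

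Three further objections have force. Treating fMRI and MRS as independent overstates the loss, because a missed or cancelled scan removes both; motion or poor spectra can still remove one alone, so the truth lies between the two patterns. The power effect is moderate, at 0.84 in the lowest case shown. And missing at random is not a uniformly weaker assumption: complete-case regression stays consistent when missingness depends on the units themselves, even on unobserved values, but not on symptoms given the units. Likelihood and imputation methods can be biased in that situation.

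These points limit the size of the concern. They do not supply a missing-data method, define the analysis set, or reconcile the power claim with the plan's own allowance.

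**Conclusion.** The point holds as a gap in the method with a cheap improvement available. Aim 1 uses procedures that by default keep only complete records, in a study that expects incomplete ones. That the analysis is restricted to complete records is inferred from the procedures' default; the plan does not say it.

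The complete-case number may fall below 68. It does so once loss exceeds about 5.3% per modality (independent) or 7.8% per visit, with no other attrition. These are conditional statements, since the rates are assumed. The firmest numerical conclusion needs no assumed failure rate: at r = 0.41 the claimed power above 0.97 is met at best by the full 80, and at the plan's own 68 it is 0.94.

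Using all observed data would lower the SD of the weights by roughly 3-13% if losses are by visit and 11-21% if independent, at 10-15% loss, under the assumed correlation and weights. The change is worth making, but the study does not depend on it.

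**What to change.** 1. Fit the Aim 1 regressions by full-information maximum likelihood (for example PROC CALIS with METHOD=FIML) or by multiple imputation (PROC MI), using all units, all symptom scores, age, sex and screening PRT.
2. Run the canonical analysis on the resulting covariance matrix, with bootstrap confidence intervals.
3. Keep the complete-case regression and canonical results as a sensitivity analysis. The two approaches rest on different missingness assumptions, so agreement between them is informative.
4. Define the Aim 1 analysis set: whether controls enter, whether patients without EEG or MRI count in the 80, and whether their session 1 scores may stand in for session 2.
5. State the expected loss for each modality and whether the 15% refers to joint completeness over all four units. Restate power at the expected analysed number.

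The cost is a revision of Section VI and modest programming, with no new data collection. The downside is reliance on data being missing at random given the observed measures, which should be stated as an assumption.
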